7.2.5. Adverse events (AE) and Serious adverse events (SAEs)

Any adverse events such as an inability to tolerate the laser therapy or a recurrence will be tracked. Since recurrence is an expected adverse event it will not be reported; however it will be monitored and if we detect an increased rate of recurrence with laser therapy, this will be reported and the trial will be stopped. Mild to moderate pain (pain score 7 or lower) secondary to laser therapy is also consider an expected adverse event and will not

be reported. SAEs due to laser treatment include severe pain (pain score 8 or higher) and deep second degree burns..

It is also possible that AE might occur that are not directly related to the study. As such, all AE will be classified as not related (clearly unrelated to study participation), possibly related (temporally related to study participation but could have been caused by other factors), or probably related (temporally related to study participation and cannot be reasonably explained by other factors) to study participation. The clinical study team will review all AE as they occur and determine the seriousness and relatedness of them.

We do not expect any severe AE in either study group. The clinical study team will review any SAE as they occur. All SAE deemed probably related to the study (and all deaths) will be reported to the IRB within 72 hours of discovery.

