1.1 Introduction

Pilonidal disease is a common problem among adolescents and young adults. It affects 26 per 100,000 people with an incidence of 1.1%.^{1,5} It is characterized by the development of epithelialized tracks and sinuses within the natal cleft extending up to the level of the coccyx posteriorly (the area between the buttocks and posterior to the anus). Entrapped hair follicles become infected resulting in acute and chronic wounds and draining sinuses that can incur both short term and long term morbidity, disability, and poor quality of life.² The most often seen initial presentation is that of a painful mass in the sacrococcygeal region.⁷ Initial treatment is usually with antibiotics and/or surgical incision and drainage of the inflamed and often infected cystic cavity. Recurrence rates have been conservatively reported at 16% and as high as 30% in some patient populations.^{2,3}

The morbidity of this disease is very significant. Patients, usually in their adolescence and young adulthood, may endure chronic pain/inflammation, drainage of sinus tracts associated with significant odor, and occasional negative-pressure wound VAC dressings which are cumbersome. When disease is active, these patients must lay prone at all times when attempting to sleep and are unable to sit due to their wounds; patients with recurrent disease report losing months to years of school and work obligations related to the treatment and chronic nature of their wounds as well as the emotional toll related to an embarrassing problem in a sensitive body area. This disease remains a source of frustration for patients and their families; they desire a durable treatment.

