7.2. Regulatory and Ethical Considerations

7.2.1. Risk Assessment

Patients will be evaluated for their skin type to ensure adequate treatment across the categories.

Laser Depilation Group

Potential risks may include:

- No relief of symptoms
- Recurrence of pilonidal abscess or wound complication

- Photosensitivity or discomfort from laser treatments
- Lastly, loss of confidentiality could be a risk.

No Laser Depilation group

- Loss of confidentiality could be a risk.

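### Sections 6.2.5 and 7.2.5 state no IRB route for a non-fatal SAE judged possibly related, so severe pain after a session can go unreported on the study team's grading alone

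*Combined protocol and SAP*

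**What the plan says.** Sections 6.2.5 (Phase One) and 7.2.5 (Phase Two) of the combined protocol and SAP carry the same text.

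- **Named SAEs:** "SAEs due to laser treatment include severe pain (pain score 8 or higher) and deep second degree burns".
- **Lesser pain:** "Mild to moderate pain (pain score 7 or lower) secondary to laser therapy is also consider an expected adverse event", and it is not reported.
- **Grades of relatedness:** all adverse events are graded not, possibly or probably related. The middle grade is "possibly related (temporally related to study participation but could have been caused by other factors"); the top grade is "probably related (temporally related to study participation and cannot be reasonably explained by other factors").
- **Who grades:** the clinical study team decides both seriousness and relatedness.
- **IRB route:** "All SAE deemed probably related to the study (and all deaths) will be reported to the IRB within 72 hours of discovery".
- **Expectation:** "We do not expect any severe AE in either study group".

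On the disease, section 1.1 says "The most often seen initial presentation is that of a painful mass in the sacrococcygeal region" and describes chronic pain and inflammation as part of its course. Sections 6.3 and 7.3 allow recruitment of patients admitted for drainage of an abscess.

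**The concern.** The IRB is the only body outside the study team to which the protocol sends individual serious events. The trigger is the team's own grade, and the top grade is demanding: another reasonable explanation is enough to rule it out. In a painful disease of the treated area, such an explanation is often at hand for pain. An SAE type that the plan itself attributes to the laser can then stay inside the team without anyone departing from the protocol. Participants are 12 to 20 years old, and no data monitoring committee or independent safety reviewer is named who would see these events by another path. At stake is timely outside notice of severe pain.

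**Working it through.** No formula is involved, so the check sets the rule beside the definitions and applies it case by case.

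**Step 1. Route by event, as 6.2.5 and 7.2.5 are worded.**

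| Event | Stated IRB route |
|---|---|
| Death, any grade | Within 72 hours |
| Non-fatal SAE, probably related | Within 72 hours |
| Non-fatal SAE, possibly related | None stated |
| Non-fatal SAE, not related | None stated |
| Laser pain scored 7 or lower | Expected; not reported |

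By this route, pain reaches the IRB only if it scores 8 or higher and is also graded *probably related*.

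**Step 2. What separates the two upper grades.** Both require a link in time with study participation, so a pain score soon after a session meets that part of either grade. The deciding test is whether another cause is available.

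**Step 3. Apply the test to the two named SAEs.** A deep burn at the laser site has few rival explanations and would ordinarily be graded *probably related*. Severe pain is different. Section 1.1 makes pain a feature of the disease, and some participants will have had an abscess drained. Section 3.3.2 excludes an actively inflamed sinus, but as an entry criterion; no section requires it to be checked again before each session. With 5 sessions 4 to 6 weeks apart (section 4), the last falls 4 × 4 = 16 to 4 × 6 = 24 weeks after the first, which leaves time for a flare. A rater could therefore reach either grade.

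**Step 4. Look for a sentence that settles it.** The list of SAEs due to the laser points to attribution to the laser. The relatedness scale, however, is said to apply to all adverse events, and the IRB sentence depends on that scale and not on the list. Nothing says which prevails.

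**Step 5. Exposure.** Phase One plans 10 patients (section 3.2.2) and the Phase Two laser arm 82 (section 5.3), each with 5 sessions: 10 × 5 + 82 × 5 = 50 + 410 = 460 sessions at most. The documents give neither a rate of scores of 8 or higher nor the share that would be graded *possibly related*, so no event count follows.

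**The case against.** The strongest case against the point is that the plan already attributes severe pain to the laser by naming it an SAE due to laser treatment, and brings in the relatedness scale after a remark about events not directly related to the study. Active inflammation is excluded at entry, and section 4 collects pain scores for 48 hours after each laser treatment. A score of 8 in that window points first to the laser, so the natural grade is *probably related*.

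Much of this stands. A reader might infer that the plan's wording forces the lower grade for nearly every severe-pain event. It does not: grading is case by case, and the list, the exclusion and the short window all favour the higher grade. What remains is that the lower grade is open to a rater who applies the definitions correctly, and that it removes the stated route.

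A reader might also infer that such events are never reported, or that the trial's safety statement rests on a filtered count. The documents support neither. The filter governs the 72-hour IRB route only. Adverse events are tracked and reviewed by the team, any suspected event goes at once to the principal investigator (6.2.4, 7.2.4), and adverse outcomes are compared between groups as a secondary objective (2.2). Pain and deep burns are primary tolerance endpoints (5.1), and the decision to proceed to Phase Two uses pain scores with no relatedness filter (5.3). These are safeguards within the study team; they do not supply outside notice of an individual event.

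**Conclusion.** The gap is real and narrow. In both phases, a non-fatal SAE graded *possibly related* has no stated IRB route, the grade is assigned by the study team alone, and the plan does not reconcile its list of laser SAEs with its relatedness scale. Of the two named SAEs, the gap mainly concerns severe pain. It affects outside oversight; it does not touch the efficacy analysis, the sample size or treatment. The number of events affected may be zero, as the plan expects, and the documents do not allow an estimate.

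The conclusion assumes that the IRB sentence means what it says and that no local reporting policy outside these documents widens it.

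The point does not extend to recurrence. Section 7.2.1 lists "Recurrence of pilonidal abscess or wound complication" as a laser-group risk and 7.2.5 does not report individual recurrences, so a reader might infer an exemption without limit. The same sentence sets a limit: a raised recurrence rate with laser therapy is to be reported and stops the trial. Recurrence is also the Phase Two primary endpoint, compared by arm. At the plan's own rates about 82 × 0.20 + 82 × 0.05 = 16.4 + 4.1 = 20.5 recurrences are expected, so reporting them singly would mean reporting endpoint events. That is debatable and is not proposed here.

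**What to change.** 1. In 6.2.5 and 7.2.5, change the IRB sentence so that it covers all SAEs deemed *possibly or probably related*, keeping all deaths and the 72 hours.
2. In the same sections, state how the list of SAEs due to laser treatment relates to the relatedness grades, so that the two passages agree.
3. In section 5.2, add a table of all SAEs regardless of relatedness: by arm in Phase Two, and overall in the single-arm Phase One. Section 4 describes the 48-hour pain reporting for the laser group, so the table should say how pain was collected in each arm.

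The first change adds two words in each of two sections; the others add a sentence or two and one table. The continuing cost is a few more IRB reports, close to none if severe events do not occur.

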7.3. Recruitment Strategy

Patients who present to Pediatric Surgery clinic will be approached to evaluate whether they would be interested in taking part in the study. In addition, patients admitted after initial surgical drainage of a pilonidal abscess will be approached to evaluate whether they would be interested in taking part in the study Risks and benefits would be explained, informed consent and assent will be obtained, and we would schedule the patient for their first treatment.

7.4. Informed Consent/Assent

All informed consents and assents will be performed by a physician-member of the research team.

If the child and legal guardian (for subjects < 18 years) are interested in participating in this study, a physician-member of the research team will guide the child and legal guardian through the informed consent/assent process. Written informed consent will be obtained from one legal guardian of subjects < 18 years of age and from the patient him or herself if he or she is ≥ 18 years of age. Written informed assent will be obtained from subjects ≥ 9 and < 18 years of age.

Refusal to participate in the study will not affect the child's clinical care. Participants and their legal guardian have the right to switch to the standard treatment and/or withdraw from the study at any time. Withdrawal from the study will not affect receipt of clinical care.

7.5. Payment to Subjects/Families

Laser depilation treatments will be provided at no cost to the patient. All clinic visits and medications related to the study will be provided at no cost to the patient.

